## 1. BACKGROUND

Prescription opioid misuse among chronic pain patients is an emerging public health threat that is being addressed with heightened urgency at both clinical and policy levels. Though opioid analgesic therapy can manage chronic pain, it may confer with significant health risks, including dependence, overdose, and misuse. Opioid misuse is evidenced by aberrant drug-related behaviors such as unauthorized dose escalation or use of prescribed opioids to self-medicate negative emotions that exacerbate craving. Research on treatments for opioid misuse among chronic pain patients is scant; according to a 2015 NIH-AHRQ systematic review of long-term opioid therapy for chronic pain, "no study evaluated the effectiveness of risk mitigation strategies for improving outcomes related to overdose, addiction, abuse, or misuse." Extant therapies may have limited efficacy because they fail to directly target cognitive-affective neural circuits that govern hedonic regulatory responses elicited by pain-, opioid-, and reward-related stimuli.8 To address this need, the PI translated mechanistic findings from behavioral neuroscience into an innovative treatment for prescription opioid misuse, called Mindfulness-Oriented Recovery Enhancement (MORE). MORE integrates training in mindfulness, reappraisal, and savoring of natural rewards to enhance hedonic regulation and target the risk chain at the point where maladaptive emotion-cognition interactions link chronic pain to opioid misuse. MORE is innovative in that it aims to modify associative learning mechanisms dysregulated by the allostatic effects of opioid misuse on brain reward systems via strengthening top-down cognitive control to restructure bottom-up reward learning from valuation of drug reward to natural reward – something that no other behavioral intervention for opioid misuse has been designed to do. Accordingly, this project funded by the National Institute on Drug Abuse (NIDA) is a randomized clinical trial (RCT) of MORE to reduce opioid misuse and chronic pain symptoms among patients receiving long-term opioid therapy in primary care.

## 2. AIMS

AIM 1. To conduct a RCT of the Mindfulness-Oriented Recovery Enhancement (MORE) intervention for co-occurring aberrant drug-related behaviors and chronic pain in primary care.

We will compare the therapeutic impact of MORE and a conventional supportive group (SG) psychotherapy active control condition on clinical outcomes germane to opioid misuse and chronic pain. Hypotheses: Opioid misusing patients assigned to MORE, as compared to SG participants, will evidence decreased opioid misuse and pain (*PRIMARY OUTCOMES*), as well as reduced opioid craving, opioid dosing, and psychological distress (*SECONDARY OUTCOMES*) from pre- to post-treatment through 9-month follow-up.

AIM 2. To test and quantify the degree to which MORE's impact on opioid misuse and pain is mediated by proactive control over emotion-cognition interactions (top-down mechanism).

Hypotheses: The impact of MORE on opioid misuse and pain will be mediated by improvements in: **a)** attentional disengagement from opioid-related cues (reduced attentional bias); **b)** emotion regulation; and **c)** cognitive coping (e.g., reinterpretation of pain as innocuous sensory information).

AIM 3. To test and quantify the degree to which MORE's impact on aberrant drug-related behaviors is mediated by restructuring of reward processing (bottom-up mechanism).

Hypotheses: The impact of MORE on aberrant drug-related behaviors will be mediated by restructured reward processing, as indicated by **a)** decreases in psychophysiological indices of opioid cue-reactivity; **b)** increases in responsiveness to natural reward cues; and **c)** a shift in the relative salience of these cues.

## 3. STUDY DESIGN

A two-arm parallel RCT design with an active control group will minimize internal threats to validity. Mindfulness-Oriented Recovery Enhancement (MORE; n=130) and the Supportive Group Psychotherapy control (SG; n=130) will be equated for time spent in treatment. Assessors will be blind to treatment condition. Target sample sizes were determined via power and precision analyses. The unit of randomization is the individual patient. The co-primary outcomes are opioid misuse and chronic pain symptoms. Participants will complete a clinical assessment battery at pre- and post-treatment, and at 3-, 6-, and 9-month follow-ups. Participants will complete a psychophysiological assessment protocol at pre- and post-treatment. Participants will complete ecological momentary assessments (EMAs) of symptoms, skill practice, and opioid use during treatment and 1 month afterward up to 3 times/day (morning, noon, and night).

## 4. ENDPOINTS

The primary, secondary, and tertiary outcome measures are summarized in Table 1.

Event	Screen	Pre -Tx	In	Post-Tx	Follow-Up			
Eveni	Screen	Pie-ix	Tx	POSI-TX	1 Mo	3 Mo	6 Mo	9 Mo
Screening and Stratification Measures								
Informed Consent	X							
Demographics & Medical History	Х							
MINI	Χ							
Primary and Secondary	Outcome N	leasures						
BPI Pain severity and interference		X		×		x	×	X
DMI: ABC, COMM & Urine screen		X		Х		Х	Х	X
Opioid dosing – TLFB and chart review		X		Х		Х	Х	X
DASS Psychological distress		X		Х		х	Х	X
Opioid Craving NRS – EMA (see below)			Х			x		
Mediators								
Self-report mediators: CSQ Reinterpretation FFMQ Mindfulness CERQ Reappraisal WOS Savoring		x		×		X	x	x
Other tertiary measures: PANAS Affect CSQ Pain Catastrophizing MLQ Meaning in Life SHAPS Anhedonia PCL PTSD Self-Transcendence		x		x		х	x	x
Psychophysiological protocol		X		×				

Intervention Process Measures and Ecological Momentary Assessments						
TMS State mindfulness (after			Х			
each session)						
Opioid craving NRS - EMA			X		X	
Opioid dosing – EMA			Χ		Χ	
Affect NRS - EMA			Χ		X	
Pain Intensity & Unpleasantness NRS - EMA			Х		x	
Therapeutic skill practice			Χ		Х	

The primary outcome is opioid misuse measured by the Drug Misuse Index, operationalized as scores on the COMM and triangulated by blinded clinical interview and urine drug screen. The co-primary outcome is chronic pain symptomology, operationalized as pain severity and functional interference scores on the Brief Pain Inventory (BPI). Overall success of the intervention will occur if opioid misuse decreases and pain functioning improves, while pain severity does not worsen. For conservatism, we evaluate all outcomes with two-sided tests, and the Bonferroni correction to control for multiple comparisons.

Primary outcomes (PRE/POST/FOLLOW-UP). Our pre-specified primary **opioid misuse** outcome in clinicaltrials.gov is a validated composite measure - the Drug Misuse Index (DMI).11 Because there is no single way to identify patients who misuse opioids. 12 the DMI uses 3 levels of data to triangulate opioid misuse: self-reports on a structured questionnaire (i.e., the COMM); clinical assessment of opioid misuse—the Addiction Behaviors Checklist (ABC)—rated by clinical staff (i.e., psychologists, social workers, and nurses) blinded to treatment assignment; and urine toxicology screens. The COMM consists of 17 items rated on a Likert scale (0=never. 4=very often) regarding how often in the past 30 days patients engaged in opioid misuse-related behaviors (e.g., used opioids in ways other than prescribed). COMM scores ≥9 and ABC scores ≥2 are considered positive. A positive rating from the urine screen is given when subjects test positive for illicit drugs or a non-prescribed opioid. Subjects with positive COMM scores will be given a positive DMI and classified as a misuser. If patients deny engaging in opioid misuserelated behavior (COMM scores <9), then positive ratings on both the urine screen and the ABC are needed for a positive DMI, because urine screens can be inaccurate due to variable drug metabolites, and clinician ratings may unreliable. 14,15 Otherwise, subjects will be given a negative DMI. Multiple studies support the validity of this DMI scoring method. 11,16–18 **Chronic** pain symptoms (pain severity and functional interference) will be assessed with the Brief Pain Inventory (BPI).

# 4.2 Secondary Outcomes

**Opioid craving** will be measured with 2 items "How much do you want to take your opioids right now?" and "How strong of an urge do have to take opioids right now?" using 0-10 Numeric Rating Scales (NRS) delivered via EMA. Single item measures of craving have been shown to validly predict opioid misuse and be sensitive to MORE treatment effects. **Reduction in opioid dose** will be assessed by the Timeline Followback Procedure (TLFB) and triangulated by chart review of prescription history by the study coordinator. Opioid dose will be converted to oral morphine-equivalent using standardized equianalgesic conversions. Subjects will also document daily opioid dose via EMA. **Psychological distress** will be measured with the Depression Anxiety Stress Scale-21 (DASS-21), a validated, reliable scale (α=.87-.94).

## 4.3 Tertiary Outcomes

The tertiary outcomes include psychophysiological measures, self-report mediators, and other EMA ratings of momentary affective state and momentary pain ratings.

## 5. RANDOMIZATION

## 5.1 Method of Randomization

An electronic random number generator will randomize participants with simple random assignment in blocks of varying sizes (2 - 4) to preserve unpredictability of allocation, which will be concealed by opaque envelopes.

All participants who met trial eligibility criteria were randomized via simple random assignment.

A computerized random number generator produced the simple random assignment. An investigator uninvolved in recruitment, consenting, assessment, or follow-up generated the assignment. No one else from the trial was involved in the process. To minimize the risk of selection bias, the investigator who generated assignments had no contact with or knowledge of study participants at the time of random assignment.

## **5.2** Allocation Concealment

Allocation concealment is an important consideration for randomized trials to control for selection bias. To prevent bias and maintain allocation concealment, participants will not be allocated until the day of the first treatment session. Assessments will be conducted by project staff blinded to group assignment (which remained concealed throughout the study). To maintain blinding, the allocation list was inaccessible to project staff involved in assessment or treatment, and before each assessment, participants were reminded to not reveal anything that would disclose their treatment assignment to study staff.

## 6. SAMPLE SIZE

# 6.1 Preliminary Data

Sample size considerations are based the effects of MORE versus SG on opioid- and pain-related variables from the Pl's NIDA R03 grant (R03DA032517). The Pl's R03-funded Stage 2 RCT identified medium to large effect sizes on pain and opioid-related variables over the course of the study (Cohen's d=.50 - .84).

## 6.2 Sample Size Determination

The table indicates the smallest detectable effects for a treatment X time interaction term given different sample sizes, assuming a Type I error rate of .05 and varying correlations between repeated measures, which ranged from .34 -.56 per outcome in the R03. Cohen defined f=0.10 and f=0.25 as small and medium effects, respectively. Thus our target N of 260 (N=200 + oversampling by 30% for attrition) will allow us to detect small-to-medium effects on continuous outcomes. Based on dichotomous clinical classification of opioid misuse data from the R03 (68% improvement for MORE versus 32% for SG), the proposed sample size will offer outstanding power (>.99) to detect differences of this magnitude on this outcome. (b) *Precision* of parameter estimation. Our target N will allow model parameters to be estimated with a high degree of precision. A per group sample size of N=130 provides 80% probability that a twosided 95% confidence interval will have a margin (half-width) less than +/- .18 standard deviation. Thus the proposed sample will provide precision more than adequate for estimating small clinical effects with high confidence. (c) *Multivariate models*. Generally, structural equation power calculations for the full information maximum likelihood sensitivity analyses can be based on Root Mean Square Error of Approximation (RMSEA) comparisons of nested models. The proposed sample provides, in a realistic testing scenario, greater than 80% power in a 1 df test (26 versus 25) of close fit comparing two models with RMSEA of .06 and .05 at  $\alpha$ =.05. These calculations are conservative. Maximum likelihood techniques retain all observations at all times, and efficiently incorporate correlated observations to yield an Effective Sample Size that is quantifiably larger than the number of subjects. With fully specified repeated dimensions, the anticipated correlations will yield an effective sample size that is 40% larger, or roughly N=360.

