**Table 2. Sample Size Estimates** 

Minimally detectable effect sizes (Cohen's f) for								
treatment X time interaction (pre-tx, post-tx, follow-up)								
Correlation	N = 100	N = 110	N = 120	N = 130				
0.25	0.16	0.15	0.14	0.14				
0.50	0.13	0.12	0.12	0.11				
0.75	0.09	0.09	0.08	0.08				

Due to COVID-19 and related research restrictions at the University of Utah, recruitment ended on March 31, 2020, with a total of 250 participants enrolled (10 participants less than the originally anticipated target N).

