, a linear combination over the four post-randomization (t>1) adjusted treatment means. The key estimand for binary DMI will be the main effect on the additive logit scale over the four post-randomization occasions.

This estimand is meaningful whether a time-by-treatment arm interaction is present or not, as it represents the expected overall treatment benefit for individuals randomly selected from the two populations. The null hypothesis of no treatment impact is  $H_{0j}$ :  $\delta_j = 0$ , a single numerator

degree-of-freedom test, which we evaluate at alpha=.05/3 = .0167 (i.e., Bonferroni adjustment for the three primary variables) under restricted maximum likelihood with Kenward-Roger denominator degrees of freedom. To control for false discovery in the three primary outcomes, we will compare the unadjusted p-values against Bonferroni-adjusted alpha =.05/3 = .0167.

The analysis of primary outcomes achieves unbiased estimates of model parameters when missingness arises from processes that depend on observed covariates (Missing at Random, or MAR). Maximum likelihood estimation (MLE) procedures under an intent-to-treat philosophy are robust against common patterns of missing data. MLE is based on all data observations; no values are deleted or imputed. In our tables and reporting, we refer to the p-values under the standard MAR assumption as pMAR. There is however no definitive test for the MAR assumption. But we investigate sensitivity to missing data and possible other covariates using two other approaches. We extend the scope of the MAR analysis using Full Information (Direct) Maximum Likelihood under broader multivariate patterns of missingness, incorporating simultaneous longitudinal outcomes and key sociodemographic variables as auxiliary variables correlated with the outcome. In simulations, this approach often yields performance equal to or better than achieved by multiple imputation and explicit nonignorable missingness models. All analyses will be conducted with the latent variable modeling program MPlus, which

incorporates full information maximum likelihood estimation in multivariate models. The global hypothesis test will be examined under three sensitivity variations:

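### Table 2 does not describe this trial: under its stated inputs the detectable effects fit N as the total sample, and at alpha .05 rather than the .0167 used; the net error is conservative

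*SAP*

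**What the plan says.** Table 2 is headed "Minimally detectable effect sizes (Cohen's f) for" the "treatment X time interaction (pre-tx, post-tx, follow-up"), that is, three occasions. Its columns are N = 100, 110, 120 and 130, and it does not say whether N is the whole trial or one arm. The rows are correlations of .25, .50 and .75. The printed values of f are .16/.15/.14/.14, .13/.12/.12/.11 and .09/.09/.08/.08.

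Section 6.2 introduces the table as "assuming a Type I error rate of .05 and varying correlations between repeated measures", and adds of the correlations, "which ranged from .34 -.56 per outcome in the R03". It takes f = .10 as small and .25 as medium, and concludes: "Thus our target N of 260 (N=200 + oversampling by 30% for attrition) will allow us to detect small-to-medium effects on continuous outcomes". No power is given for the table. The only nearby power for a hypothesis test belongs to the structural equation calculation: "greater than 80% power in a 1 df test (26 versus 25").

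Section 3 plans 130 patients per arm, and the precision statement in section 6.2 also treats 130 as the size of one group. Section 4 says of testing: "we evaluate all outcomes with two-sided tests, and the Bonferroni correction to control for multiple comparisons". Section 8.3 sets the level for the null hypothesis on each primary variable, "which we evaluate at alpha=.05/3 = .0167 (i.e., Bonferroni adjustment for the three primary variables"). Two of those three variables are the continuous pain severity and pain interference scores. The test there has 1 degree of freedom and concerns the treatment difference averaged over the four post-randomization visits, conditional on baseline.

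**The concern.** Table 2 is the only detectable-effect calculation for the continuous co-primary variables. A reader will take its columns as arm sizes, because 100 and 130 are exactly half of 200 and 260 and the SAP uses 130 as an arm size elsewhere. If the cells were computed with those numbers as the whole trial, no column belongs to this trial, and the step from the table to the target of 260 does not follow from the figures shown.

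Separately, the table uses a level three times as large as the one in the primary analysis. That mismatch between sections 6.2 and 8.3 stands on the text alone, however N is read. What is at stake is whether the SAP gives a correct account of what the trial can detect at the level at which it will be judged.

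**Working it through.** **Inputs.** Two arms (section 3); m = 3 occasions and correlations r = .25, .50, .75 (Table 2); alpha .05 (section 6.2) or .05/3 = .0167 (section 8.3). Power of 80% is my assumption.

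**Step 1: reproduce the table.** For a treatment-by-time interaction in a two-group repeated-measures design with sphericity, the noncentral F test has

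- df1 = (2 − 1)(m − 1) = 2 and df2 = (N − 2)(m − 1), with N the total sample;
- noncentrality λ = N·m·f²/(1 − r), so f = √[λ(1 − r)/(N·m)].

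Example: for N = 100 and alpha .05, df2 = 196 and 80% power needs λ = 9.78. With r = .25, f = √(9.78 × .75/300) = .156, printed as .16.

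| r | Printed, N = 100/110/120/130 | N as total | N per arm (totals 200/220/240/260) |
|---|---|---|---|
| .25 | .16/.15/.14/.14 | .156/.149/.143/.137 | .110/.105/.100/.097 |
| .50 | .13/.12/.12/.11 | .128/.122/.116/.112 | .090/.086/.082/.079 |
| .75 | .09/.09/.08/.08 | .090/.086/.082/.079 | .064/.061/.058/.056 |

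With N as the total, 12 of 12 cells match to two decimals. With N per arm, 0 of 12 match, and the same holds at 85, 90 and 95% power.

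**Step 2: the trial's totals at the level used.** At N = 200 and alpha .0167 the required λ rises from 9.71 to 12.69, so f rises by √(12.69/9.71) = 1.14, about 14%.

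| r | N = 200 | N = 250 | N = 260 |
|---|---|---|---|
| .25 | .126 | .113 | .110 |
| .50 | .103 | .092 | .090 |
| .75 | .073 | .065 | .064 |

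Each value lies below every printed value in its row (smallest printed: .14, .11, .08). Doubling N divides f by about √2 = 1.41 and the stricter level multiplies it by 1.14. The net factor is 1.14/1.41 = .81.

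For the correlations seen in the earlier trial, .34 and .56, f at alpha .0167 is .118 and .096 (N = 200), and .103 and .085 (N = 260).

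**Step 3: the test actually planned.** Step 2 still concerns an interaction over three occasions. For the baseline-adjusted contrast averaged over four visits, with compound symmetry and a common standard deviation, the adjusted variance of a patient's mean is v = (1 + 3r)/4 − r² in squared standard deviations. With equal arms and a normal approximation, d = (z for the two-sided level + z for the power) × √(4v/N). At alpha .0167 and 80% power the sum is 2.394 + .842 = 3.236.

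- r = .34: v = .505 − .1156 = .3894; at N = 200, d = 3.236 × √(1.5576/200) = .286.
- r = .56: v = .670 − .3136 = .3564; at N = 200, d = 3.236 × √(1.4256/200) = .273.
- At N = 250 the two values are .255 and .244; at N = 260 they are .250 and .240.

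**The case against.** The strongest reply is that the reading of N is an inference. Table 2 states no power, so a reader might infer too much in saying that the cells can arise only with N as the total. With N per arm, all 12 cells also match at three occasions, alpha .0167 and 95% power; at two occasions, alpha .05 and 95% power; and at three occasions, alpha .05 and about 98.1 to 98.5% power. The first two contradict an input that the SAP states, and the third is not a conventional power. A lower-bound sphericity correction (epsilon .5) at about 87 to 88.5% power matches as well, but the SAP mentions no such correction. This part of the reply stands: total N at 80% is the most natural reading, not the only possible one. Under either of the first two alternatives the SAP would still misdescribe its own table.

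The second reply is that nothing harmful follows. A reader might infer that a halved N and a looser level add up to an underpowered trial. They do not; they offset, and the balance favours the trial. That reply stands in full.

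A third tempting step is to convert the interaction f to a standardized difference. If d is the same at both later visits and zero at baseline, f² = d²/18. At N = 200 and alpha .0167 this gives d of about .50 (r = .34) to .41 (r = .56). That is not what the primary test can detect, because section 8.3 does not test this interaction.

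Finally, 250 is the enrolment reached when recruitment closed on 31 March 2020, not a planning size, so its absence from Table 2 is no fault.

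**Conclusion.** The concern holds as a fault in the sizing figures, not in the size of the trial. Under the stated level and number of occasions and an assumed 80% power, Table 2 gives detectable effects for trials of 100 to 130 patients in total. Independently of that assumption, it uses .05 where section 8.3 uses .0167. For totals of 200 to 260 at .0167, the detectable interaction f is about four fifths of the tabled figure, so the conclusion that small to medium effects are detectable is not false. It is not supported by the numbers cited for it. For the planned primary contrast, the detectable difference at N = 200 is about d = .27 to .29. That range assumes compound symmetry, correlations of .34 to .56, equal arms and 80% power.

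**What to change.** In section 6.2 and Table 2, label N as the total sample (after checking the source calculation), state the power, and give the detectable effects at total N = 200 and 260, and at 250 as enrolled, with alpha .0167. If the interaction is kept, the second table in the working supplies the values under 80% power. To support the primary analysis, base the restated figure on the section 8.3 contrast (1 degree of freedom, averaged over four post-baseline visits, adjusted for baseline), state the assumed correlation structure, and word the conclusion in terms of that effect. The cost is one table and a few sentences in the SAP. Conduct, enrolment and the planned analyses are unaffected.

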**Table 2. Sample Size Estimates** 

Minimally detectable effect sizes (Cohen's f) for								
treatment X time interaction (pre-tx, post-tx, follow-up)								
Correlation	N = 100	N = 110	N = 120	N = 130				
0.25	0.16	0.15	0.14	0.14				
0.50	0.13	0.12	0.12	0.11				
0.75	0.09	0.09	0.08	0.08				

Due to COVID-19 and related research restrictions at the University of Utah, recruitment ended on March 31, 2020, with a total of 250 participants enrolled (10 participants less than the originally anticipated target N).

